12.0 CRITERIA FOR DISCONTINUATION OF THERAPY

Treatment will be stopped for grade 4 acute toxicity (according to the current version of Common Terminology Criteria for Adverse Events (CTCAE version 4), but may be resumed per protocol if the treatment break is less than 10 working days. If grade 4 toxicity resolves beyond the 10 days the treating physician will decide whether to give additional RT.

Treatment will be stopped if metastasis is detected by radiographic or pathologic evidence and the patient will be removed from the study. A work-up for metastasis during treatment will only be carried out if the treating physician deems necessary.

Patients may discontinue therapy at the treating physician's discretion, i.e. due to non-compliance. Patients may withdraw their consent at any time.

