4.11 Duration of Therapy

- The therapy will be delivered over approximately 7– 8 weeks.
- Treatment will be stopped for grade 4 acute toxicity (according to the current version of Common Terminology Criteria for Adverse Events (CTCAE version 4), but may be resumed per protocol if the treatment break is less than 10 working days. Since we have never observed grade 4 toxicity acutely using IMRT such an event is unlikely. If grade 4 toxicity resolves beyond the 10 days the treating physician will decide whether to give additional RT.
- Treatment will be stopped if metastasis is detected by radiographic or pathologic evidence and the patient will be removed from the study, but not from intent-to-treat analysis. A work-up for metastasis during treatment will only be carried out if the treating physician deems necessary.
- In case that the 2-year MRI exam identifies a suspicious for cancer lesion, US-guided biopsies will be taken.

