5.2 Evaluations during Radiation Therapy

- Weekly history and physical including performance status (Zubrod), and toxicity.

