5.4 Post-treatment Evaluations

- History and physical, performance status (Zubrod), and toxicity at 6 weeks, 3 months, and then every 6 months for 5.25 years after completion of RT.
- Blood (up to 5 tubes) work in relation to RT:
 - PSA at 6 weeks, 3 months, and then every 6 months for 5.25 years.
 - Serum total testosterone 9 months after completion of RT.
 - Blood for research fluid tests will be collected at 3 months, 9 months and 2-2.5 years after completion of RT.
- DCE-MRI and or PET with timed contrast at 3 months, 9 months, and 2-2.5 years after completion of RT.
 - Should a lesion be identified, the treating physician will discuss management decisions with the participant
- Bone scan for a PSA of ≥ 2 or physician concern for metastasis.
- Psychosocial questionnaires will be administered at follow-up at 6 weeks, 3 months, 9 months, 15 months and yearly to 5.25 years:
 - Memorial Anxiety Scale for Prostate Cancer patients (MAX-PC).
 - The Expanded Prostate Cancer Index Composite Questionnaire-SF-12 (EPIC-SF12).

- International Prostate Symptom Scale (IPSS) will be done at each follow-up visit for 5.25 years. This includes 6 weeks, 3 months and every 6 months after RT for 5.25 years.

Note: Measurements and follow-up visits should occur within \pm 2 weeks up to the 3 months visit and within \pm 8 weeks for subsequent measurements/visits

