5.5 Early Discontinuation of Therapy

See Criteria for Discontinuation of therapy in section 12.0.

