9.1 Definitions

- *PSA response rate*: The proportion of study patients with PSA <0.1 ng/mL at 21 months after completion of study treatment.
- *Acute toxicity*: Toxicity occurring during treatment and within three months of completing treatment.
- *Late toxicity*: Toxicity occurring more than three months after treatment completion. *Failure rate*: The cumulative incidence of biochemical or clinical failure allowing for competing risk as needed. Clinical failure is defined as at least a 25% increase in the size of the tumor relative to the smallest volume recorded, or new extension of tumor beyond the capsule, or re-extension of tumor beyond the capsule after initial regression, or urinary obstructive symptoms with carcinoma found at TURP. Biochemical failure is defined as PSA \geq nadir + 2 ng/mL.

- *Failure-free Survival (FFS)*: The elapsed time from start of radiotherapy to first documented evidence of biochemical or clinical failure or death from any cause, whichever occurs first. In the absence of any event defining failure, follow-up time will be censored at the date of last documented failure-free status.
- *Overall Survival (OS)*: The elapsed time from start of radiotherapy to death from any cause. For surviving patients, follow-up will be censored at the date of last contact.
- *Biomarker expression*: Quantification of the amount of the biomarker specific immunohistochemical staining in the area of tumor.
- *QOL*: Two contemporary instruments will be utilized to assess patient function and bother (Expanded Prostate Cancer Index Composite-SF12 (EPIC-SF12) and prostate cancer-specific anxiety Memorial Anxiety Scale for Prostate Cancer patients (MAX-PC).

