Evaluable: Patients who are study eligible and receive an initial dose of *MTSRT* will be considered *evaluable for safety*, regardless of whether or not the full course of radiation treatment is completed according to protocol. To be *evaluable for efficacy*, study eligible patients must either (1) complete radiation treatment and the nine month post treatment PSA assessment or (2) initiate therapy but develop evidence of biochemical or clinical failure, or die from causes related to prostate cancer, within nine months of stopping or completing treatment. In the latter case (2), which is expected to be rare, patients will be included as non-responders in the evaluation of PSA response rate. The set of patients who are evaluable for efficacy comprise the main analysis set.

Exclusions: Any patient who is enrolled on study but does not receive an initial dose of radiation treatment will be excluded from all efficacy analyses. Any patient who initiates treatment and is later found to be ineligible for study (e.g., protocol violation) will be withdrawn from study but will be followed for toxicity and clinical outcome; the experience of such patients will be characterized separately from that of patients who are evaluable for efficacy. Reasons for exclusion of enrolled patients from analysis of safety or efficacy will be characterized.

Study endpoints are defined in **Section 9.1**.

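### Men with metastasis found during RT are removed from the study with no stated follow-up, and toxicity visits and windows have no anchor date for any man who does not complete RT

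*Combined protocol and SAP*

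**What the plan says.** - **Removal.** Section 12.0: "Treatment will be stopped if metastasis is detected by radiographic or pathologic evidence and the patient will be removed from the study". Section 4.11 gives the same rule, with the man "removed from the study, but not from intent-to-treat analysis". Section 12.0 lacks that last clause. Metastasis is the only finding for which either section removes a man from the study.
- **Safety set.** Section 14.3 makes an eligible man evaluable for safety after one dose, "regardless of whether or not the full course of radiation treatment is completed according to protocol".
- **Early discontinuation.** Section 5.5 consists of a cross-reference, "See Criteria for Discontinuation of therapy in section 12.0". Section 12.0 contains no follow-up schedule.
- **Visits.** During RT, Section 5.2 requires "Weekly history and physical including performance status (Zubrod), and toxicity". Afterwards, Section 5.4 schedules "toxicity at 6 weeks, 3 months, and then every 6 months for 5.25 years after completion of RT".
- **Windows.** Section 9.1 defines acute toxicity as "Toxicity occurring during treatment and within three months of completing treatment". Late toxicity begins more than three months after completion. Section 14.6 uses the same division for its stopping rules.
- **Contrasts within Section 14.3.** The efficacy definition counts failures within nine months of either stopping or completing treatment. Treated men later found ineligible "will be withdrawn from study but will be followed for toxicity and clinical outcome".

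**The concern.** An eligible man whose RT is stopped for metastasis has been exposed to the boost and belongs to the safety set, yet the text ends his participation without saying that anyone will look for late toxicity or record his death. A treated man later found ineligible has better-defined follow-up than he does, and nothing in the plan explains the difference.

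The second gap is wider. A man who stops RT for any reason and does not resume never reaches completion, so his 6-week, 3-month and later visits, the end of his acute window and the start of his late window have no defined date.

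Two things are at stake. Toxicity monitoring is the only formal early-stopping mechanism in this single-arm trial, and its boundaries are set in single patients. Also, men who progress during treatment are plausibly at higher risk of death than the rest, so losing them is unlikely to be neutral for overall survival and prostate-cancer mortality.

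**Working it through.** **1. What the text provides for three kinds of treated men**

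| Treated man | Safety set (14.3) | Stated follow-up after he stops | Anchor for visits and acute/late windows |
|---|---|---|---|
| Eligible, metastasis during RT | Yes | None; removed from the study | None |
| Eligible, RT stopped for another reason and not resumed | Yes | Not removed; no schedule in 5.5 or 12.0 | None |
| Later found ineligible | Described separately | Toxicity and clinical outcome | Completion, if reached |

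The intent-to-treat clause in 4.11 does not fill the first row. It concerns who is analysed, not what is collected, and Section 14 defines no intent-to-treat set.

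**2. Reproducing the plan's figure**

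Inputs from Section 14.6: prior Beta(0.2, 1.8) for the late G3+ rate; stop if the posterior probability that the rate exceeds 10% is at least 80%.

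Formula: P(rate > 0.10 | x events in n men) = 1 − F(0.10; 0.2 + x, 1.8 + n − x), where F is the beta distribution function.

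For 2 of 8 this is 1 − F(0.10; 2.2, 7.8) = 82.6%, as the plan states.

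**3. Effect of one man**

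| Situation | x/n | Posterior beta | P(rate > 10%) | Guideline |
|---|---|---|---|---|
| Full follow-up | 2/8 | (2.2, 7.8) | 82.6% | Stop |
| One event unseen, man still counted | 1/8 | (1.2, 8.8) | 47.9% | Continue |
| One event unseen, man dropped from the count | 1/7 | (1.2, 7.8) | 52.5% | Continue |
| An unfollowed ninth man counted as event-free | 2/9 | (2.2, 8.8) | 79.1% | Continue |

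Dropping the unfollowed man from the denominator does not restore the decision if his event was one of the two.

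**4. Average effect on the late rule**

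The documents give no number of affected men, so 1, 2 or 4 of 40 is assumed. The late rule was simulated (40,000 trials, true late rate 20%, boundary checked after each patient from the third, unfollowed men chosen at random). The probability of ever stopping by 40 patients was:

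| Unfollowed men | Counted as event-free | Left out of the count |
|---|---|---|
| 0 | 90% | 90% |
| 1 | 89% | 90% |
| 2 | 88% | 89% |
| 4 | 85% | 87% |

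Because the unfollowed men were drawn at random, the simulation does not cover the case where stopping is related to toxicity risk.

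**The case against.** Much of the plan works against a broad reading.

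- **A reader might infer that these men have no toxicity follow-up.** They do have some. Toxicity is assessed weekly during RT (5.2), the acute window includes the treatment period, and SAEs are followed to resolution, an acceptable medical endpoint or loss to follow-up (11.3.3). What is missing is scheduled assessment after stopping; following a known SAE does not detect a new late event.
- **A reader might infer that every early stopper is lost.** Only metastasis triggers removal. A man stopped for treatment-related grade 4 GI or GU toxicity is already an acute G3+ event under 14.6. For him the gap is an undefined date for later visits and the late window.
- **A reader might infer that lost men count as non-events in the cumulative incidence.** Section 14.5 starts that analysis at treatment start, and Table 14.5 censors at last contact and treats subsequent therapy as a competing risk. The late rule is illustrated on men with sufficient follow-up. Dilution of the stopping rule arises only if removed men are counted as evaluated, which the plan leaves open.
- **A reader might want a figure for the bias in the final late rate.** The documents give neither the number of early stoppers nor their late toxicity rate. The 10% drop-out in 14.2 concerns evaluability for PSA response.
- **Survival.** Section 14.5 says patients are followed for progression and vital status for five years, and it classes distant spread as clinical failure, so failure rate and failure-free survival capture the event that causes removal.

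These points stand and limit the concern. They do not supply follow-up after removal or an anchor date. The general five-year statement in 14.5 conflicts with removal from the study in 4.11 and 12.0, and the plan does not say which prevails. Censoring at last contact is unbiased only if leaving is unrelated to later risk, which is doubtful for men who leave because of metastasis.

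**Conclusion.** The concern holds in a limited form. The plan keeps a treated man with metastasis in its safety set while removing him from the study with no stated toxicity or survival follow-up, and Sections 4.11 and 12.0 differ on his place in the analysis. For any man who does not complete RT, post-treatment visits and the acute/late division have no anchor. As written, late toxicity, overall survival and prostate-cancer mortality are informatively censored for the removed men.

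The size is probably small. With 1 to 4 of 40 men affected (an assumption), the chance of stopping at a true late rate of 20% falls from 90% to between 89% and 85% if they are counted as event-free, and by less if they are left out. A single man can nonetheless reverse a decision at the boundary. The documents support neither a quantified bias in the final toxicity rates nor a statement that toxicity in these men goes unrecorded altogether. This is a worthwhile, inexpensive correction, not a flaw that undermines the design.

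**What to change.** 1. Reconcile 4.11 with 12.0, so that both say a man with metastasis found during RT is off protocol treatment but remains in toxicity, failure and survival follow-up unless he withdraws consent, and both say the same about the analyses in which he is included.
2. In 5.4, 5.5, 9.1 and 14.6, run visits and the acute and late windows from the date of the last fraction delivered, for every man who received at least one fraction.
3. In Table 14.6.1, define the number of patients evaluated, for each rule, as men who have either the required follow-up or an event.

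The treatment-start origin in 14.5 should stay. The rules on when RT is stopped or resumed are not part of this point and need no change. The cost is protocol wording and, for a few men, follow-up visits that already exist in the schedule.

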13.0 DATA REPORTING

Data must be submitted according to the protocol requirements for ALL patients registered. Patients for whom documentation is inadequate to determine eligibility will generally be deemed ineligible.

14.0 STATISTICAL CONSIDERATIONS

Up to 80 participants will be accrued for the entire study (Phase II and Phase III). The study is currently in Phase II which will accrue up to 40 participants. For a description of the statistical considerations of the Phase III component of the trial, please refer to protocol version 7.0, dated 10/14/2015.

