3.3.2 Cancellation Guidelines

If a patient does not receive protocol therapy, the patient may be withdrawn from the study. Patients who are enrolled on study but not treated will be excluded from all analyses.

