14.1 Overview

This is a single-arm Phase II trial with the primary objective of determining whether MRI-targeted boost SRT (MTSRT) improves the rate of PSA response (i.e., PSA < 0.1 21 months post treatment completion) in men receiving radiation therapy due to rising PSA post-prostatectomy. Secondary objectives include evaluation acute and late occurring toxicity, quality of life, biochemical and clinical failure, and survival. Additionally, blood and biopsy tissue samples from study patients will provide data for various biomarker studies described in the Bankhead Coley Team Science project "Integrated biomarkers for individualized prostate cancer therapy".

A single stage design without interim analysis of the primary endpoint is proposed for this trial because it would not be practical or desirable to suspend accrual to accommodate an interim assessment of PSA response, which requires nine months follow-up. Moreover, PSA response is not a perfect near term surrogate for long term benefit and thus not a definitive basis for an early conclusion regarding efficacy. The trial involves standard therapy with dose escalation, and an evaluation of PSA response based on accrual of 40 evaluable patients will provide information needed to design a subsequent trial evaluating long term outcome. Early stopping rules based on monitoring the toxicity of study treatment are provided in Section 14.6.

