14.2 Sample size, accrual rate and study duration

Sample size is based on the primary objective of demonstrating that MTSRT increases the rate of PSA response to treatment, by which we mean undetectable PSA level (<0.1) when assessed 21 months after completing treatment. We expect the PSA response rate in the standard SRT to be 60%. [50] Assuming sufficient follow-up to determine PSA nine months post treatment, a total of 40 patients in the single-arm study provides 83.9% power to detect an absolute increase of 20% in the PSA response rate, from 60% to 80%, using a one-sided Fisher's exact test with 5% significance level. To ensure a minimum of 40 study patients evaluable for PSA response as our main study endpoint, we plan to enroll a total of 44 patients assuming 10% drop-out.

We plan to accrue 1 patient per month during the first year of this protocol. After the ramp-up phase is completed, we anticipate 1.5 patients per month. This rate was also calculated considering increasing prostate cancer volumes due to expansion of the department (anticipated growth at Sylvester main and Deerfield branch). Thus accrual will be complete in about 3 years; 12 in year 1 and 18 per year in year 2 and 3. Patients will be followed for a minimum of five years, giving total study duration of 8 years. The main efficacy endpoint will be analyzed after enrollment is complete and all patients have been

assessed for PSA response nine months post treatment, and a final efficacy analysis of all endpoints will be carried out at the conclusion of study when patients have been followed for 5 years. Analyses of some secondary endpoints, including acute toxicity, psychosocial parameters, and biomarker distribution on US guided biopsies, and initial MRI findings may be reported before the efficacy analyses. These secondary endpoints will be analyzed after all planned patients have been accrued, completed treatment and have a minimal potential follow-up of 3 months from the end of RT.

14.3 Definitions and endpoints:

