To illustrate the stopping guidelines, suppose that 4 patients have been assessed for toxicity and 3 of them have experienced grade 3 treatment-related toxicity during or within 3 months of completing radiotherapy (second row, left panel). Under this circumstance, the observed rate of acute G3+ toxicity is 37.5%, resulting in a posterior probability of 90.4% that the true underlying rate exceeds 15% thus suggesting early termination of the study due to acute toxicity. Similarly for late G3+, suppose that a total of 8 patients have been followed sufficiently for assessment of late toxicity and 2 have experienced grade 3 treatment-related toxicity starting more than 3 months after treatment completion (first row, right panel). These data give a 25% observed rate of late G3+ toxicity and a posterior probability of 82.6% that the true underlying rate exceeds 10% thus suggesting early termination of the study due to late toxicity.

Posterior probabilities used to derive guidelines for acute toxicity are calculated under a prior beta distribution with parameters $\beta_1 = 0.3$ and $\beta_2 = 1.7$, which corresponds to an expected rate of 15% based

on prior information roughly equivalent to having studied 2 patients. Furthermore, this prior distribution assigns a small a priori chance (32%) to the possibility that the true rate of unacceptable toxicity is 15% or greater. For late toxicity, the parameters of the prior distribution are $\beta_1 = 0.2$ and $\beta_2 = 1.8$, giving an a priori chance of 27% that the true rate of late toxicity is 10% or greater.

No early stopping for efficacy. We do not propose early stopping of this trial based on interim assessment of efficacy for the following reasons. First, it would not be practical or desirable to suspend accrual to accommodate an interim assessment of the primary efficacy endpoint, PSA response, which requires nine months follow-up. Moreover, PSA response is not a perfect near term surrogate for long term benefit and thus not a definitive basis for an early conclusion regarding efficacy. The trial involves standard therapy with dose escalation, and an evaluation of PSA response based on accrual of 24 evaluable patients will provide information needed to design a subsequent trial evaluating long term outcome.

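### Phase II enrolment is capped at 40 in 3.0 and 14.0, while 14.2 plans to enrol 44 to obtain 40 evaluable men; one figure is needed

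*Combined protocol and SAP*

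**What the plan says.** - **3.0 Patient Selection and 14.0 Statistical Considerations** carry the same sentence: "The study is currently in Phase II which will accrue up to 40 participants". It stands beside a ceiling of 80 participants for Phases II and III together.
- **14.2** gives the design calculation: "a total of 40 patients in the single-arm study provides 83.9% power", for an increase from 60% to 80% with a one-sided 5% test. It then plans for losses: "we plan to enroll a total of 44 patients assuming 10% drop-out". The stated purpose of that allowance is to have no fewer than 40 men who can be assessed for the primary endpoint. The same section projects 12 men in year 1 and 18 in each of years 2 and 3.
- **14.1** also treats 40 as the evaluable number: "an evaluation of PSA response based on accrual of 40 evaluable patients will provide". The matching sentence in **14.6** has a different count: "an evaluation of PSA response based on accrual of 24 evaluable patients will provide information".
- **14.3** makes evaluability for efficacy narrower than enrolment: "study eligible patients must either (1) complete radiation treatment and the nine month post treatment PSA assessment", or else fail or die of prostate cancer early after starting treatment. **3.3.2** adds: "Patients who are enrolled on study but not treated will be excluded from all analyses".
- **Table 14.6.1** gives toxicity stopping boundaries for up to 40 evaluated patients. Under 14.3, every eligible man who receives a first dose counts for safety.

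**The concern.** Three enrolment figures for the same phase stand in current text: 40 (3.0, 14.0), 44 (14.2) and 48 (the sum of the 14.2 schedule). A site that stops at 40 departs from 14.2. A site that continues to 44 exceeds the ceiling in 3.0 and 14.0, the figure a site or ethics board would be expected to apply. The plan offers its 44 as the allowance that secures 40 evaluable men, and its power is quoted for 40. A hard stop at 40 removes that allowance. At stake are an enforceable ceiling, the promised minimum of 40 evaluable and, to a lesser degree, the stated power.

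**Working it through.** **Inputs.** Null 60%, target 80%, one-sided 5%, 40 analysed, power 83.9%, drop-out 10%, enrolment 44, and accrual of 1 per month for 12 months then 1.5 per month (all 14.2); cap 40 (3.0, 14.0); toxicity priors and the 80% posterior rule (14.6).

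**1. The plan's power.** For n analysed, take the smallest r with P(X ≥ r | n, 0.60) ≤ 0.05; power is P(X ≥ r | n, 0.80). At n = 40, r = 29 has size 0.0709 (too large) and r = 30 has size 0.0352. Power is 0.8392, which matches 83.9%. The figure therefore belongs to 40 analysed men and comes from an exact one-sample binomial test, although 14.2 names Fisher's exact test.

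**2. The plan's enrolment figure.** 40 × 1.10 = 44, as stated. Dividing by the retained fraction gives 40 / 0.90 = 44.4, rounded up to 45.

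**3. Evaluable men at 10% drop-out.** Assume independent drop-out, so evaluable ~ Binomial(N, 0.9).

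| Enrolled N | Expected (0.9N) | P(at least 40 evaluable) |
|---|---|---|
| 40 | 36.0 | 0.9^40 = 1.5% |
| 44 | 39.6 | 54.7% |
| 45 | 40.5 | 70.8% |

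**4. Power at the realised number** (same test, r re-derived at each n).

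| n | r | Size | Power |
|---|---|---|---|
| 35 | 27 | 0.0260 | 74.5% |
| 36 | 27 | 0.0449 | 83.2% |
| 37 | 28 | 0.0348 | 80.9% |
| 38 | 29 | 0.0268 | 78.4% |
| 39 | 29 | 0.0450 | 85.9% |
| 40 | 30 | 0.0352 | 83.9% |

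The function is saw-toothed, so power at one n can mislead. Averaging, Σ P(n evaluable | N) × power(n), gives:

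| Drop-out | 40 enrolled | 44 enrolled |
|---|---|---|
| 5% | 81.9% | 85.3% |
| 10% | 79.5% | 83.3% |
| 15% | 77.0% | 81.0% |

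At the plan's 10% the difference is 83.3 − 79.5 = 3.8 points.

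**5. Sidedness.** Section 14.5 says that tests are two-sided at 5%. With 2.5% in the upper tail, power at n = 40 is 73.2%. Averaged over 10% drop-out it is 67.1% (40 enrolled) v 72.4% (44). Any restated power must therefore name its test.

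**6. Accrual.** 40 men: 12 + (40 − 12)/1.5 = 30.7 months. 44 men: 12 + (44 − 12)/1.5 = 33.3 months. The difference is 4/1.5 = 2.7 months, and both fall within the projected three years or so. The schedule itself allows 12 + 18 + 18 = 48.

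**7. Table 14.6.1 beyond 40.** With x events in n men, the posterior is Beta(0.3 + x, 1.7 + n − x) for acute toxicity (limit 15%) and Beta(0.2 + x, 1.8 + n − x) for late toxicity (limit 10%). The plan's late example, 2 of 8, reproduces at 82.6%.
- Late: 6 of 40 gives 80.4%, so the boundary is 6, as tabulated. 6 of 41 gives 78.9% and no longer meets the rule. 7 of 41 gives 89.6% and 7 of 44 gives 86.2%, so the boundary is 7 for 41–44.
- Acute: 9 of 40 gives 87.5% and 9 of 44 gives 80.8%, while 8 of 41 gives 75.1%. The boundary stays at 9 for 41–44.

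**The case against.** **The cap may count evaluable men.** A reader might infer that 3.0 and 14.0 cannot mean this. That is too strong. Section 14.1 speaks of accruing 40 evaluable men, and 14.2 calls the same 40 simply patients before explaining that 44 are enrolled to reach them. Sections 14.3 and 3.3.2 show that the two counts differ; they do not show which one the cap uses. The enrolled reading is still the more natural, because the sentence says participants, sits under patient selection in 3.0, and stands beside a whole-study ceiling in the same unit. Nothing says that replacements fall outside the cap.

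**The trial may look underpowered.** A reader might take 79.5% as a failed target. The plan sets no 80% benchmark; it only reports 83.9%. At exactly the expected 36 evaluable, power is 83.2%, a loss of 0.7 points. That value is a favourable tooth of the saw, which is why the average is shown beside it. On either measure the loss is modest, so this is mainly a conflict over the enrolment ceiling.

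**Safety monitoring may look untouched.** The posterior rule does work at any number of patients, as 14.6 says. The printed table stops at 40, however, and the late boundary changes at 41, so choosing 44 requires an edit there.

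**Conclusion.** The inconsistency is real and worth correcting: 3.0 and 14.0 cap Phase II at 40 participants, 14.2 plans 44, and the 14.2 schedule sums to 48. If enrolment closes at 40, the stated minimum of 40 evaluable is reached only if nobody is lost, a 1.5% chance at the plan's own drop-out rate. Even 44 gives only about an even chance (54.7%), so the minimum is expected rather than assured.

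The probabilities assume independent 10% drop-out, and the power figures also assume the one-sided exact binomial test; step 4 gives averaged power for 5% to 15%. The plan leaves open when that drop-out is counted: 14.3 judges evaluability at nine months, while 9.1 and 14.2 place the endpoint at 21 months. The intended evaluable number, 40, is not in doubt. The 24 in 14.6 conflicts with the parallel sentence in 14.1 and needs only an editorial correction.

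**What to change.** **Preferred: adopt 44.**
1. Change the Phase II cap in 3.0 and 14.0 to 44 and state that it counts enrolled men.
2. In 14.2, replace the assured minimum with about 40 evaluable expected (39.6). If an expectation of at least 40 is wanted, enrol 45 instead.
3. Align the yearly accrual figures with the chosen total.
4. Confirm that the whole-study ceiling of 80 still holds. The documents do not give the number accrued before version 8.0, so this cannot be checked here.
5. Extend Table 14.6.1 to 41–44 under the stated priors and 80% rule: acute boundary 9, late boundary 7. With 45 enrolled, add a row for 45, where 9 acute events give 78.9% and the acute boundary becomes 10.
6. Change the 24 in 14.6 to the 40 of 14.1.

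*Cost:* at most 4 men above the 40 cap, none beyond the 44 already planned, and about 2.7 months of accrual. Choosing 45 adds one more man.

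**Alternative: keep 40.** Delete the 44 and the minimum of 40 evaluable from 14.2. Restate power for the expected 36 evaluable, with the drop-out-averaged figure beside it (83.2% and 79.5% under the one-sided exact binomial test). Name the test and sidedness, because 14.2 and 14.5 differ. Items 3 and 6 still apply.

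*Cost:* no extra men, but the plan gives up its minimum of 40 and about 3.8 points of averaged power relative to 44.
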